9.2 Sample Size Determination

The sample size for this trial was estimated using CreoStat HB StudySize software, v3.0.2. Using a log rank, two-sided, non-parametric Proportional Hazards (Freedman) approach, with accrual time assumed to be zero, α set to 0.025, 1- β set to 0.90, wound "survival" in the control arm set to 60% (thus 40% healed), and wound "survival" in the TTAX01 arm set to 35% (thus 65% healed), assuming 1:1 randomization and a 10% dropout, it is estimated that 94 subjects per group will be needed. As an added margin, 110 will be enrolled per group in the US portion of the trial (increases power to 94%). Three additional sites in Taiwan are expected to participate in this multicenter trial, but consistency of data between the US and TW sites is unknown. Therefore, the TW sites will be allowed to enroll 10 subjects per site, for an additional 30 subjects overall (15 per arm). This raises the power to 97%, assuming all data are acceptable for analysis.

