9 STATISTICAL CONSIDERATIONS

9.1 Statistical Hypotheses

• Primary Efficacy Endpoint(s):

The primary efficacy endpoint is time in weeks from baseline to the initial observation closure of a complete wound healing, over 26 weeks, that is confirmed at two consecutive visits each two weeks apart. The primary efficacy endpoint will be analyzed using the Cox regression analysis (i.e., proportional hazards model) to assess the effect of TTAX01 treatment on time to complete wound healing compared to SC in terms of hazard ratio and difference in the curve of the proportion of subjects reaching the complete wound healing over the 26-week treatment period.

The null hypothesis is that the hazard ratio of TTAX01 arm vs, SC arm is not statistically different from 1.0. The alternative hypothesis is that the hazard ratio is lower than 1.0 at the significance level of <0.05.

• Secondary Efficacy Endpoint(s):

Secondary efficacy endpoints in this study include proportions of index ulcers healed by Week 50, proportions of wound re-ulcerations by Week 50, proportions of minor and major amputations by Week 50, and total score of PROMIS Lower Extremity Function Questionnaire at end of study.

For index ulcer healing by Week 50, the null hypothesis is that the proportion of subjects with wound healing will not be statistically different between the two treatment arms of this study at Week 50. The alternative hypothesis is that a greater proportion of subjects in the SC plus TTAX01 arm will have index ulcers healed at Week 50, compared to the SC alone arm.

For index ulcer re-ulceration by Week 50, the null hypothesis is that, among those subjects who have had the index ulcer healed before Week 50, the proportion of subjects with wound re-ulcerated will not be statistically different between the two treatment arms of this study at

Week 50. The alternative hypothesis is that a smaller proportion of subjects in the SC plus TTAX01 arm will have index ulcers re-ulcerated at Week 50, compared to the SC alone arm.

For minor and major amputations by Week 50 following initial procedure, the null hypothesis is that the proportion of subjects receiving minor and/or major amputations will not be statistically different between the two treatment arms of this study by Week 50. The alternative hypothesis is that a smaller proportion of subjects in the SC plus TTAX01 arm will have minor and/or major amputations by Week 50, compared to the SC alone arm.

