9.3 Populations for Analyses

The Intent-to-Treat (ITT) population will consist of all enrolled and randomized subjects. The ITT population is the primary efficacy population and will be used to conduct all analyses on primary and secondary efficacy endpoints.

The Per Protocol (PP) population is a subset of subjects in the ITT and is the secondary efficacy population. The PP population will be defined as all qualified and treated subjects meeting inclusion and exclusion criteria and completing the study treatment as planned in the protocol, with no major protocol deviations during the 26-week Treatment Period. Major protocol deviations will be determined by the trial clinical team prior to database lock. Subjects found to have major protocol deviations will be excluded from the PP population.

The Safety Population includes all subjects who underwent treatment, regardless of protocol compliance. The Safety Population will be used for the analyses of safety endpoints.

The Long-Term Observation (LO) Population includes all subjects who entered the long-term observation period of Visits 22 thru 26. The Long-Term Observation Population will be used for the analyses of those efficacy and safety endpoints that are assessed over the long-term observation period.

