9.4 Statistical Analyses

9.4.1 General Approach

All data will be presented using summary statistics or frequency tables, as appropriate, and will be analyzed for superiority comparisons between SC plus TTAX01 arm and SC alone arm for both the treatment period and long-term observation period. The description of the sample will be done using summary statistics (n, mean, standard deviation, median, and maximum/minimum) for continuous data and using frequency statistics (counts and percentages) for categorical data. Hypothesis testing, unless otherwise indicated, will be performed at the 5% significance level (2-sided). All *P*-values will be rounded to four decimal

places; *P*-values less than 0.0001 will be presented as '<0.0001' in all tables. Unless specifically stated, all confidence intervals will be two-sided with 95% coverage.

The Sponsor, or their designee, will analyze the data using SAS® Statistical Analysis System Version 9.1.3 or higher. Detailed descriptions of the statistical analysis methods, data conventions, and sensitivity analysis as well as handling of missing data for both efficacy and safety measures will be described in detail in the Statistical Analysis Plan (SAP).

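### Section 9.2 labels the sample size as two-sided α = 0.025, but its 94 per group and 94% power follow from two-sided α = 0.05

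*Protocol*

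**What the plan says.** Section 9.2 gives the method and level as a "two-sided, non-parametric Proportional Hazards (Freedman) approach, with accrual time assumed to be zero, α set to 0.025". The other inputs are 90% power, 60% of control wounds and 35% of TTAX01 wounds still open, 1:1 randomization and 10% dropout. The result is 94 per group. The section raises this to 110 per group in the US, with 94% power, and then adds 15 per arm from Taiwan: "This raises the power to 97%, assuming all data are acceptable for analysis".

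The analysis sections use another level. Section 9.1 says of the primary endpoint: "The alternative hypothesis is that the hazard ratio is lower than 1.0 at the significance level of <0.05". Section 9.4.1 says that hypothesis testing, unless otherwise indicated, "will be performed at the 5% significance level (2-sided"), with 95% confidence intervals. Section 9.4.2 reports a 95% interval for the hazard ratio. Section 9.4.6 plans no interim analysis.

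**The concern.** Section 9.2 attaches the word two-sided to 0.025, whereas Sections 9.1 and 9.4.1 use 0.05. There is one primary endpoint and no interim look, so nothing in the protocol explains a halved level. If the label in 9.2 were right, the stated size would miss its own 90% target and all three powers would be too high. If the label is wrong, the α reported for the sample size of a confirmatory trial is wrong. Either way, a reader who recomputes 9.2 as written will not get 94.

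**Working it through.** **Inputs (all from Section 9.2).** Unhealed 0.60 (control) and 0.35 (TTAX01); power 0.90, z = 1.2816; 1:1 allocation; 10% dropout; zero accrual time, taken to mean that everyone has full follow-up. Two-sided critical values: 1.960 for α = 0.05 and 2.2414 for α = 0.025.

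**Effect size.** HR = ln 0.35 / ln 0.60 = 2.0551. Freedman factor: ((1 + HR)/(1 − HR))² = (3.0551/1.0551)² = 8.384.

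**Sample size.** Events = (z_α + z_β)² × 8.384. Per group, n = events / (2 − 0.60 − 0.35) = events / 1.05, then divided by 0.90 for dropout.

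- Reproducing the protocol's 94, with two-sided 0.05: (1.960 + 1.2816)² × 8.384 = 88.1 events; 88.1/1.05 = 83.9; 83.9/0.90 = 93.2, so 94. Rounding up to 84 before the dropout step also gives 94.
- As labelled, with two-sided 0.025: (2.2414 + 1.2816)² × 8.384 = 104.1 events; 104.1/1.05 = 99.1; 99.1/0.90 = 110.1, so 111 (112 if 99.1 is first rounded up to 100). Even without any dropout allowance, 100 per group exceeds 94.
- One-sided 0.05, as another possible source: 71.8 events, 69 per group, 77 after dropout. This does not give 94 either.

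**Power.** Expected events d = 0.90 × n × 1.05, with n per group. Power = Φ(√d × 1.0551/3.0551 − z_α).

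| Per group | d | Stated | Two-sided 0.05 | Two-sided 0.025 |
|---|---|---|---|---|
| 94 | 88.8 | 90% | 90.2% | 84.5% |
| 110 | 104.0 | 94% | 94.1% | 90.0% |
| 125 | 118.1 | 97% | 96.4% | 93.5% |

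At the labelled level the stated powers are too high by 5.5, 4.0 and 3.5 points. At two-sided 0.05 the first two agree and the third is 0.6 points high. Treating dropout as n/1.1 instead of 0.90n gives 96.5% at 125, which would round to 97%. That convention gives 93 per group, not 94 (83.9 × 1.1 = 92.3).

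**The case against.** The strongest reply is that nothing in the trial depends on the label. The analysis sections agree on 5%, the intervals are 95%, and at that level the size delivers the power claimed. The figure 0.025 appears once, as a planning input, and equals the per-tail value of two-sided 0.05. This stands, and it limits the point to a misstatement in 9.2.

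A second reply is that other methods come near the stated figures at two-sided 0.025. Schoenfeld's formula without dropout gives 92 per group, and 90.9%, 94.8% and 97.0% power at 94, 110 and 125. A simulated log-rank test with exponential times and 10% random dropout gives 89.2%, 93.8% and 96.0% (95.93%). So the shortfall at 0.025 belongs to the Freedman formula, which is conservative here. These results do not rescue 9.2. The first drops both the named method and the stated dropout; the second is not the named method and falls just short of 90% at 94. Freedman's formula with the stated dropout gives exactly 94 at two-sided 0.05.

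Two stronger readings are tempting. A reader might infer that the trial is underpowered; at the 5% level set for the analysis, it is not. A reader might also take the condition that all data be acceptable as permission to drop the Taiwan subjects after seeing the results, with a higher false-positive rate. The protocol does not support that. The clause qualifies a power figure. Section 9.3 makes ITT the primary efficacy population and defines it: "The Intent-to-Treat (ITT) population will consist of all enrolled and randomized subjects". No section provides a US-only primary analysis or a rule for choosing between the two sets.

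**Conclusion.** The point holds as an error of statement. With the named method and all stated inputs, two-sided α = 0.025 does not produce 94 per group (it needs 111 or 112) or the stated powers. Two-sided α = 0.05 produces 94 exactly, with 90.2% and 94.1% power, and 96.4% where the protocol says 97%. The most likely explanation is a per-tail 0.025 described as two-sided. That is an inference from the match and from Sections 9.1 and 9.4.1; the text does not say it.

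The figures assume Freedman's formula, full follow-up, and dropouts who contribute no events. The 97% is a minor matter, since its 0.6-point gap is no larger than a change of dropout convention or rounding can produce.

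**What to change.** In Section 9.2, replace the level with: *two-sided α = 0.05 (0.025 in each tail)*. Restate power as 90% at 94, 94% at 110 and 96% at 125 per group.

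If two-sided 0.025 is really intended, give 111 or 112 per group as the size for 90% power, restate 84%, 90% and 93% at 94, 110 and 125, and change Sections 9.1 and 9.4.1 and the confidence level of the intervals to match. The planned 110 per US group would then just reach 90%.

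Optionally, reword the condition on the Taiwan data so that it agrees with Section 9.3, where all randomized subjects form the primary population.

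The first option costs a wording change in one paragraph and one slightly less favourable power figure. Neither option needs more patients.

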9.3 Populations for Analyses

The Intent-to-Treat (ITT) population will consist of all enrolled and randomized subjects. The ITT population is the primary efficacy population and will be used to conduct all analyses on primary and secondary efficacy endpoints.

The Per Protocol (PP) population is a subset of subjects in the ITT and is the secondary efficacy population. The PP population will be defined as all qualified and treated subjects meeting inclusion and exclusion criteria and completing the study treatment as planned in the protocol, with no major protocol deviations during the 26-week Treatment Period. Major protocol deviations will be determined by the trial clinical team prior to database lock. Subjects found to have major protocol deviations will be excluded from the PP population.

The Safety Population includes all subjects who underwent treatment, regardless of protocol compliance. The Safety Population will be used for the analyses of safety endpoints.

The Long-Term Observation (LO) Population includes all subjects who entered the long-term observation period of Visits 22 thru 26. The Long-Term Observation Population will be used for the analyses of those efficacy and safety endpoints that are assessed over the long-term observation period.

9.4 Statistical Analyses

9.4.1 General Approach

All data will be presented using summary statistics or frequency tables, as appropriate, and will be analyzed for superiority comparisons between SC plus TTAX01 arm and SC alone arm for both the treatment period and long-term observation period. The description of the sample will be done using summary statistics (n, mean, standard deviation, median, and maximum/minimum) for continuous data and using frequency statistics (counts and percentages) for categorical data. Hypothesis testing, unless otherwise indicated, will be performed at the 5% significance level (2-sided). All *P*-values will be rounded to four decimal

places; *P*-values less than 0.0001 will be presented as '<0.0001' in all tables. Unless specifically stated, all confidence intervals will be two-sided with 95% coverage.

The Sponsor, or their designee, will analyze the data using SAS® Statistical Analysis System Version 9.1.3 or higher. Detailed descriptions of the statistical analysis methods, data conventions, and sensitivity analysis as well as handling of missing data for both efficacy and safety measures will be described in detail in the Statistical Analysis Plan (SAP).

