For total score of CWIS and PROMIS Questionnaires, the null hypothesis is that a total score (or better quality-of-life) of this measure will not be statistically different between the two treatment arms of this study at the end of study. The alternative hypothesis is that a greater total score (or better quality-of-life) of one or both of these measures will be seen for the SC plus TTAX01 arm at the end of study, compared to the SC alone arm.

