9.4.3 Analysis of the Secondary Endpoints

Secondary efficacy endpoints in this study include proportions of index ulcer healed by Week 50, proportions of wound re-ulcerations by Week 50, proportions of minor and major amputations by Week 50, and total score of PROMIS Lower Extremity Function Questionnaire at end of study.

The non-parametric Cochran-Mantel-Haenszel (CMH) test with adjustment for baseline wound size cohort will be used to examine treatment effects for the SC plus TTAX01 arm vs. SC alone arm on proportion of subjects with index ulcer achieving and remaining healed at Week 50, proportion of subjects (among those with complete wound healing before Week 50) with wound re-ulceration at Week 50, and proportion of subjects with minor and/or major amputations by Week 50. Subjects' missing values at Week 50 in these endpoints, due to either no assessment or early termination from the study, will be imputed using the last-observation carry forward (LOCF).

An analysis of covariance model (ANCOVA) with treatment and baseline wound size as effect will be used to analyze total score of PROMIS Lower Extremity Function Questionnaire at end of study. Subjects' missing values in this endpoint, due to either no assessment or early termination from the study, will utilize the assessment collected at the early termination visit.

The analyses of the secondary efficacy endpoints will be performed for the ITT population and PP population as well as the LO population.

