9.4.9 Exploratory Analyses

None.

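### The protocol's written default tests four secondary efficacy hypotheses at two-sided 5% each, with no gate on the primary, no order, no alpha split and no supportive label

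*Protocol*

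**What the plan says.** Protocol Section 9.4.1 describes the analyses in general as superiority comparisons between the arms and gives one default level: "Hypothesis testing, unless otherwise indicated, will be performed at the 5% significance level (2-sided"). It then leaves detailed methods, data conventions, sensitivity analyses and missing-data handling to the SAP. Multiplicity is not among the topics it names.

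Section 9.1 writes a null and a directional alternative for each secondary endpoint. For durability of closure, for example: "The alternative hypothesis is that a smaller proportion of subjects in the SC plus TTAX01 arm will have index ulcers re-ulcerated at Week 50". PROMIS is paired there with the Cardiff schedule (CWIS), and the pair's alternative can be met by either score: "The alternative hypothesis is that a greater total score (or better quality-of-life) of one or both of these measures".

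Section 9.4.3 lists the family, beginning "Secondary efficacy endpoints in this study include proportions of index ulcer healed by Week 50, proportions of wound re-ulcerations by Week 50". It assigns Cochran-Mantel-Haenszel tests to healing, to re-ulceration and to the "proportion of subjects with minor and/or major amputations by Week 50", and an analysis of covariance that "will be used to analyze total score of PROMIS Lower Extremity Function Questionnaire at end of study". It adds: "The analyses of the secondary efficacy endpoints will be performed for the ITT population and PP population as well as the LO population".

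Section 9.3 names ITT as the primary efficacy population and PP as the secondary one. The section headed "9.4.9 Exploratory Analyses" states that there are none.

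**The concern.** Section 2.1 presents this as a confirmatory trial, and Section 6.3 says site staff are not blinded. The secondary endpoints carry clinical weight: Section 2.3.2 expects fewer major amputations as a long-term benefit, and Section 3 links amputation to lost mobility and higher mortality.

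The protocol is not silent on how these endpoints are tested. It gives each one hypotheses, a test and a level, and the only level that applies is 5% per test. Under that rule any one of the four nulls can be rejected at p<0.05 whatever happens to the other three or to the primary. A reader of the final report could then take an isolated result on amputation or re-ulceration as demonstrated, although the chance of at least one such result arising by luck is well above the level stated for a single test.

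**Working it through.** **Inputs.**
- Level per test: two-sided 0.05 (Section 9.4.1).
- Number of tests: four (Section 9.4.3), each in ITT, the primary efficacy population (Section 9.3).
- CWIS is not counted, because Section 3 lists it under safety.
- Correlation between the four test statistics: not given in the protocol. It is assumed here to be common to all pairs and varied from 0 to 0.7.

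**Step 1. The plan's own figure.** The protocol states no family-wise error rate for the secondaries, so there is none to reproduce. The figure that does depend on alpha is the sample size in Section 9.2, which shows the level used for the primary.
- Hazard ratio = ln(0.35)/ln(0.60) = 2.055.
- Freedman events = (1.960 + 1.282)² × [(1 + 2.055)/(1 − 2.055)]² = 10.51 × 8.38 = 88.1, so 89.
- Average healing proportion = (0.40 + 0.65)/2 = 0.525, so 89/0.525/2 = 84.8, or 85 per arm.
- With 10% added for dropout: 93.5, so 94 (dividing by 0.9 gives 95). The protocol states 94.

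The match needs a critical value of 1.96. The primary is therefore sized at the full two-sided 5%, and no part of that 5% is set aside for the secondaries.

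**Step 2. Four independent tests, all nulls true.**
- Any rejection: 1 − 0.95⁴ = 1 − 0.8145 = 18.5%.
- Any rejection in favour of TTAX01: 1 − 0.975⁴ = 1 − 0.9037 = 9.6%, against 2.5% for one test.

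**Step 3. Correlated tests.** The statistics are taken as Z_i = √ρ·C + √(1−ρ)·E_i, with C and E_i independent standard normal, oriented so that positive values favour TTAX01. The chance that any |Z_i|, or any Z_i, exceeds 1.96 was simulated with 2 million draws per row.

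| Assumed common correlation | Any false rejection | Any false rejection favouring TTAX01 |
|---|---|---|
| 0 | 18.5% | 9.6% |
| 0.2 | 18.0% | 9.1% |
| 0.3 | 17.4% | 8.7% |
| 0.4 | 16.5% | 8.3% |
| 0.5 | 15.6% | 7.8% |
| 0.6 | 14.4% | 7.2% |
| 0.7 | 13.0% | 6.5% |

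**Step 4. With control.** Holm on four tests compares the ordered p-values with 0.0125, 0.0167, 0.025 and 0.05. With all four nulls true, a rejection needs the smallest p-value to be below 0.0125. If the tests are independent the rate is 1 − (1 − 0.0125)⁴ = 4.9%. At a correlation of 0.5 it is 4.3%. Holm stays at or below 5% whatever the correlation.

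**The case against.** The strongest reply is that secondary multiplicity is commonly settled in the SAP, which is not at hand. Section 9.4.1 sends detailed methods there, and its 5% level applies only where nothing else is indicated. A 5% default is also compatible with a fixed sequence, where every step is tested at 5%. This stands. It means no one can infer from the protocol that the trial lacks multiplicity control. What remains is that the protocol itself writes a per-test rule for formally stated hypotheses and points to nothing that modifies it.

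Second, no sentence says that a secondary p<0.05 counts as a claim, or counts after a failed primary. That is also right. It follows from applying the written rule, not from an explicit statement. The absence of planned exploratory analyses does not by itself make the secondaries confirmatory.

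Third, Section 3 describes Week 50 healing and re-ulceration as giving insight, which is the language of supportive endpoints. It is not a formal label, though, and the amputation and PROMIS rows have nothing similar.

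A reader might also infer three larger effects that the documents do not support:
- **Twelve tests, from four endpoints in three populations.** Section 9.3 already makes ITT the primary efficacy population, and nothing says that a win in any population would be claimed.
- **A single rate of about 16%.** This arises only at a common correlation of roughly 0.4 to 0.5, which the protocol does not give. A common correlation is itself doubtful, because re-ulceration is tested only among subjects who healed.
- **Benefit declared falsely at three times the stated 5%.** The two-sided rate counts rejections in both directions. False findings of benefit run from 7.8% (correlation 0.5) to 9.6% (independent). The proper comparison for these is 2.5%.

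**Conclusion.** The point holds as a criticism of the protocol's written default. Four secondary efficacy endpoints have directional superiority hypotheses and a test each, and the only stated level is two-sided 5% per test. With all four nulls true, the chance of at least one false rejection is 18.5% under independence and about 18% to 13% for assumed common correlations of 0.2 to 0.7. For false findings favouring TTAX01 it is about 9.6% (independent) to 7.8% (correlation 0.5), against a nominal 2.5%.

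These rates assume that TTAX01 has no effect on any of the four endpoints, and they rest on correlations that the protocol does not supply. The primary endpoint's own error rate is not affected. Because the SAP may already contain a procedure, this is a cheap improvement to make and not a defect in the trial's main conclusion.

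**What to change.** State one of the following in Section 9.4.3, with a matching reference in Sections 9.1 and 9.4.1:

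1. Secondary efficacy claims are made only if the primary ITT test is significant. The four ITT secondary tests (healing, re-ulceration, minor and/or major amputation as one endpoint, PROMIS) then follow the Holm procedure at an overall two-sided 5%. PP, LO and Section 9.4.7 subgroup results are supportive and carry nominal p-values.
2. If no secondary claims are intended, all four secondary endpoints are descriptive.
3. If the SAP already holds a multiplicity procedure, the protocol refers to it.

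The cost is a few sentences before database lock, with no added subjects or data. The price is that an isolated secondary result that misses its Holm threshold (for the smallest p-value, anything from 0.0125 to 0.05), or any secondary result after a failed primary, can no longer be claimed as confirmatory.
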